Permitted Medications	
If a subject receives inadequate analgesia from study treatment and allowed rescue medication, they may terminate from the efficacy portion of the study and receive open-label standard of care analgesia excluding NSAIDs or gabapentinoids as per the discretion of the investigator. At the time of receiving standard of care analgesia, the following assessments will be performed prior to receiving standard of care analgesia:
 
 
• NPRS
 
• PGA
 
• PK sample
 
 
Because subjects will remain in the unit and continue to have all other assessments performed there is no need to do anything else at this time. If a subject is not willing to remain in the unit, then they should have all assessments as detailed in the current protocol language for early termination.
 
Subjects who terminate early due to lack of efficacy will continue to receive their allotted study treatment and will continue to undergo all safety and pharmacokinetic assessments as scheduled. These subjects will also continue with all scheduled follow up visits (unless the subject withdraws consent). Subjects who withdraw because of an AE, would not continue to receive study medication.
 
Antiemetics
 
No pretreatment for potential nausea and vomiting is permitted. Administration of antiemetic medications are limited to subjects with active vomiting, subjects with a score <math>\geq 5</math> on the NNRS, or by subject request only.

Study Objectives:	Primary Efficacy

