	
 
To evaluate the efficacy of high dose XG005 [1250 mgQ12] compared to placebo for pain control in subjects undergoing bunionectomy
 
 
Secondary Efficacy
 
 
To evaluate the efficacy of low dose XG005 [750 mg Q12] compared to placebo for pain control in subjects undergoing bunionectomy
 
To evaluate high and low dose XG005 compared to placebo for total rescue consumption and time to first use from end of surgery
 
To evaluate high and low dose XG005 compared to placebo for PGA
 
To evaluate high and low dose XG005 compared to placebo for postoperative nausea
 
To evaluate the efficacy of high dose XG005 compared to low dose XG005 for pain control in subjects undergoing bunionectomy
 
 
Tertiary Efficacy (All Treatment Arms)
 
 
To evaluate rescue medication consumption at 24, 48, and 72 hours, time to first use of rescue medication from end of surgery, and proportion of subjects requiring rescue medication.
 
To evaluate nausea assessment scores at various timepoints
 
To evaluate high and low dose XG005 compared to placebo for SIS
 
 
Exploratory
 
 
To estimate subject's potential placebo response by use of a pre-study personality questionnaire at Screening
 
 
Safety and Tolerability
 
 
To evaluate the safety and tolerability of XG005 in a perioperative population
 
 
Pharmacokinetics
 
 
To investigate the PK of XG005 in a perioperative population
 

Primary Efficacy Endpoint:	Summed pain intensity from end of surgery to 48 hours post-surgery (SPI48) for high dose XG005 vs placebo

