Secondary Endpoints:	
Key Secondary Endpoints:
 
 
SPI48: low dose XG005 vs placebo
 
Total tramadol rescue medication consumption in morphine equivalents (MEQs) over 48 hours: high dose XG005 vs placebo
 
Total tramadol rescue medication consumption in morphine equivalents (MEQs) over 48 hours: low dose XG005 vs placebo
 
 
Additional Endpoints:
 
 
Time to first use of rescue medication from end of surgery: high dose XG005 vs placebo
 
Time to first use of rescue medication from end of surgery: low dose XG005 vs placebo
 
PGA at 48 hours: high dose XG005 vs placebo
 
PGA at 48 hours: low dose XG005 vs placebo
 
Cumulative Nausea (NNRS) assessment scores through 24 hours: high dose XG005 vs placebo
 
Cumulative Nausea (NNRS) assessment scores through 24 hours: low dose XG005 vs placebo
 
SPI48: high dose XG005 vs low dose XG005
 

Tertiary Endpoints:	
Tertiary Endpoints for All Treatment Arms:
 
 
Total rescue medication consumption at 24, 48, and 72 hours
 

	
 
• Nausea (NNRS) assessment scores at 1, 4, 8, 12, 24, 48, and 72 hours
 
• SPI at 0, 1, 2, 3, 4, 6, 8, 10, 12, 16, 20, 24, 30, 36, 42, 48, 54, 60, 66, and 72 hours
 
• Pain intensity at various timepoints
 
• SIS at 24, 48 and 72 hours
 
• Percentage of subjects requiring rescue at various timepoints
 
• PGA of pain control at various timepoints
 
• Ramsay Sedation Scale at various timepoints
 
 
Exploratory:
 
 
• Estimate of subject susceptibility to placebo response at Screening using a pre-study personality questionnaire
 

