- o) Subjects will be permitted rescue medication throughout the 72-hour inpatient domiciling period as follows to manage breakthrough pain only if it occurs while domiciled: IV acetaminophen 1 g, will be administered Q 6 hours, PRN, up to 4 g in 24 hours. If a patient is unable to tolerate acetaminophen or if there is insufficient pain relief, 50 mg tramadol will be administered Q 4 hours, PRN, up to 300 mg in 24 hours. Study staff will record the time and the dose of rescue medication administered on the rescue medication form. NPRS and PK sampling will be collected immediately prior to administering rescue medication. Only the protocol-defined rescue medication is permitted in the study.
- p) Study staff will record subject-reported pain assessments via a standard 11-point NPRS at the following time points post-end of surgery: 0, 1, 2, 3, 4, 6, 8, 10, 12, 16, 20, 24, 30, 36, 42, 48, 54, 60, 66, and 72 hours within a  $\pm 10$ -minute window ([Appendix C](#)). NPRS will be collected prior to PK sampling and administration of rescue medication.
- q) Pain intensity assessments scheduled between 24:00 and 06:00 may be skipped if the subject is sleeping. However, consecutive pain assessments may not be skipped, and the Hour 12, Hour 24, and Hour 48 pain assessments must be completed even when they fall asleep between 24:00 and 06:00.
- r) Study staff will record subject-reported PGA of pain control using a 5-point scale (poor, fair, good, very good, excellent) at the following time points post-end of surgery: 24, 48, and 72 hours within a  $\pm 10$ -minute window and just prior to receiving a dose of rescue medication ([Appendix D](#)). PGA will also be performed and recorded at early termination.

- s) Nausea will be measured after the end of surgery by using the 11-point NNRS at the indicated time points with a  $\pm$  10-minute window ([Appendix E](#)). PK sampling blood draws will always be performed after NNRS assessment. Additional NNRS time points will be collected when an AE of nausea or vomiting is reported or prior to any rescue antiemetic medication. Administration of antiemetic medications are limited to subjects with active vomiting, subjects with a score  $\geq 5$  on the NNRS, or by subject request only. No pretreatment for potential nausea and vomiting is permitted.

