### 3. OBJECTIVES AND ENDPOINTS

Objectives	Endpoints
Primary Efficacy:	

 
To evaluate the efficacy of high dose XG005 [1250 mg Q12] compared to placebo for pain control in subjects undergoing bunionectomy.
 
	
 
Summed pain intensity from end of surgery to 48 hours post-surgery (SPI48) for high dose XG005 vs placebo
 

Secondary Efficacy:	

 
To evaluate the efficacy of low dose XG005 [750 mg Q12] compared to placebo for pain control in subjects undergoing bunionectomy.
 
To evaluate high and low dose XG005 compared to placebo for total rescue consumption and time to first use from end of surgery.
 
To evaluate high and low dose XG005 compared to placebo for PGA
 
To evaluate high and low dose XG005 compared to placebo for postoperative nausea.
 
To evaluate the efficacy of high dose XG005 compared to low dose XG005 for pain control in subjects undergoing bunionectomy
 
	
Key Secondary Endpoints:
 
 
SPI48: low dose XG005 vs placebo
 
Total tramadol rescue medication consumption in MEQs over 48 hours: high dose XG005 vs placebo
 
Total tramadol rescue medication consumption in MEQs over 48 hours: low dose XG005 vs placebo
 
 
Additional Analgesic Endpoints:
 
 
Time to first use of rescue medication from end of surgery: high dose XG005 vs placebo
 
Time to first use of rescue medication from end of surgery: low dose XG005 vs placebo
 
PGA at 48 hours: high dose XG005 vs placebo
 
PGA at 48 hours: low dose XG005 vs placebo
 
Cumulative nausea (NNRS) assessment scores through 24 hours: high dose XG005 vs placebo
 
Cumulative Nausea (NNRS) assessment scores through 24 hours: low dose XG005 vs placebo
 
SPI48: high dose XG005 vs low dose XG005
 

Tertiary Efficacy (All Treatment Arms):	

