### **6.5.2. Rescue Medication**

During the domiciling period, subjects may be administered IV acetaminophen 1 g, Q 6 hours, PRN, up to 4 g in 24 hours. If a patient is unable to tolerate acetaminophen or if there is insufficient pain relief, 50 mg tramadol will be administered Q 4 hours, PRN, up to 300 mg in 24 hours. Intravenous acetaminophen should always be the first rescue medication administered with tramadol being used as the second option.

Prior to receiving any rescue medication, an NPRS assessment must be performed immediately before administering any rescue medication.

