### **6.5.4. Permitted Medications**

Only the protocol-defined rescue medication is permitted in the study. All other analgesics administered will result in a subject terminating early from the study.

No pretreatment for potential nausea and vomiting is permitted. Administration of antiemetic medications are limited to subjects with active vomiting, subjects with a score  $\geq 5$  on the NNRS, or by subject request only.

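### Key secondary endpoints 2 and 3 count tramadol rescue only, so a non-tramadol opioid given after a switch to open-label analgesia adds nothing to the 48-hour MEQ total

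*Combined protocol and SAP*

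**What the plan says.** - **Endpoint.** Key secondary endpoint 2 in the Synopsis is "Total tramadol rescue medication consumption in morphine equivalents (MEQs) over 48 hours: high dose XG005 vs placebo". Section 3 repeats it as "Total tramadol rescue medication consumption in MEQs over 48 hours: high dose XG005 vs placebo". Endpoint 3 is the low-dose counterpart.
- **Objective.** The matching secondary objective is "To evaluate high and low dose XG005 compared to placebo for total rescue consumption and time to first use from end of surgery".
- **Rescue.** IV acetaminophen comes first. Section 6.5.2 then allows tramadol: "50 mg tramadol will be administered Q 4 hours, PRN, up to 300 mg in 24 hours". Tramadol is the only opioid among the protocol-defined rescue drugs. Footnote o to the Schedule of Assessments says: "Subjects will be permitted rescue medication throughout the 72-hour inpatient domiciling period".
- **Switch.** Under Permitted Medications in the Synopsis, if study treatment and rescue are not enough, "they may terminate from the efficacy portion of the study and receive open-label standard of care analgesia excluding NSAIDs or gabapentinoids". Opioids are neither named nor excluded.
- **Status of other analgesics.** Section 6.5.4 keeps them apart from protocol-defined rescue: "All other analgesics administered will result in a subject terminating early from the study".
- **Missing data.** Section 9.5.5 replaces pain scores after rescue with the last score before it, and assigns WOCF to data missing after discontinuation for an adverse event or lack of efficacy. It does not say what WOCF means for a cumulative drug amount.
- **Deferred detail.** Sections 9, 9.5.2 and 9.5.5 leave further detail to a separate SAP, which is not part of the text reviewed.

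**The concern.** The subjects allowed to switch are those in whom study drug and rescue have both failed. They are also the subjects in whom opioid use may move out of the category that endpoints 2 and 3 count. The omission is therefore related to outcome. If switching, or what follows it, differs between arms, the tramadol-only comparison no longer reflects the difference in opioid use.

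Section 2.4 gives lower opiate use as part of the study rationale, and the endpoint is expressed in morphine equivalents. Many readers will therefore take a result on endpoint 2 as evidence about opioid sparing. The endpoint also sits early in the serial procedure of Section 9.3, so a falsely non-significant result would close every later test.

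**Working it through.** **1. The plan's own figure.** Section 9.2 states 90% power with 130 evaluable subjects per arm at a standardized effect of 0.40, two-sided alpha 0.05.

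Power = Φ(0.40 × √(130/2) − 1.960) = Φ(3.225 − 1.960) = Φ(1.265) = 0.897. The stated figure reproduces. It is the plan's only sample-size calculation, and it gives no SD or effect for the MEQ total.

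**2. What the endpoint can count.** From Section 6.5.2: 300 mg / 50 mg = 6 doses per 24 hours. Over 48 hours that is 12 doses, or 600 mg. The countable amount runs from 0 to 600 mg of tramadol. A non-tramadol opioid contributes 0 at any dose. Conversion to MEQs multiplies every subject's total by one tramadol factor, so it changes no ordering.

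**3. Does a switcher score lower than a subject who stays on rescue?** Take a switcher with 2 tramadol doses (100 mg) in the first 12 hours. Compare subjects who stay on rescue and take 3 to 12 doses (150 to 600 mg).

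| Rule (none is stated) | Switcher's total | Against 150 to 600 mg |
|---|---|---|
| No tramadol after the switch, no imputation | 100 mg | Lower than all |
| Post-switch tramadol occurs and counts | 100 mg plus whatever is taken | Undetermined |
| WOCF by 12-hour interval (assumed form) | 4 × 100 = 400 mg | Higher than 3 to 7 doses, equal to 8, lower than 9 to 12 |

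The ordering depends on a rule that the documents do not give.

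**4. Effect on the between-arm difference.** Let p be the share of an arm that switches before 48 hours, and U the mean uncounted non-tramadol MEQs per switcher. U carries both timing and amount. Subscript P is placebo and A is an XG005 arm.

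Tramadol-only difference (placebo minus XG005) = all-source difference − (pP × UP − pA × UA)

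- pP × UP larger: the XG005 advantage is understated.
- pA × UA larger: it is overstated.
- Products equal, or no non-tramadol opioid used: the mean difference is unchanged.

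The documents give no value for p or U, so the bias cannot be calculated.

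**5. Illustration on assumed inputs only.** Assume a true all-source effect of 0.40 SD, 130 per arm, the same U in both arms, and the SD held fixed. Then observed effect = 0.40 − (pP − pA) × U.

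| Placebo vs XG005 switch rate | U = 0.5 SD | U = 1 SD | U = 2 SD |
|---|---|---|---|
| 5% vs 2% | 0.385 (power 87%) | 0.370 (85%) | 0.340 (78%) |
| 10% vs 5% | 0.375 (86%) | 0.350 (81%) | 0.300 (68%) |
| 20% vs 10% | 0.350 (81%) | 0.300 (68%) | 0.200 (36%) |
| 10% vs 10% | 0.400 (90%) | 0.400 (90%) | 0.400 (90%) |

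The table shows how the effect depends on the inputs; it does not estimate what this trial will see. With the rates reversed (5% placebo, 10% XG005, U = 1 SD) the observed effect would be 0.40 + 0.05 = 0.45.

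**6. Place in the hierarchy.** Section 9.3 uses the Section 3 order: 1 primary + 3 key secondary + 7 additional = 11 tests. Endpoint 2 is test 3, and 11 − 3 = 8 tests follow it. If only the key secondary endpoints were meant, it would be test 3 of 4 with one test after it.

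**The case against.** **The endpoint measures what it says.** The plan's stated quantity is tramadol rescue. Against that quantity, an opioid outside rescue is outside the definition and there is no bias. This stands in part: choosing all-source opioid use is a choice of estimand, and the sponsor may keep tramadol-only. It does not remove the need to show whether a result on that endpoint also holds for opioid use.

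**The objective does not settle it.** A reader might infer from the objective's reference to total rescue that open-label opioids ought to count. The documents do not support this. By Section 6.5.4 open-label analgesia is not rescue, so it lies outside the objective too. The gap between objective and endpoint is acetaminophen, which is a different matter.

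**Treatment failures may not score better.** A reader might infer that a switcher necessarily ranks ahead of a subject who stays on tramadol. Step 3 of the working shows that this depends on whether post-switch tramadol counts and on how WOCF is applied. The WOCF sentence in Section 9.5.5 is not limited to pain scores, so it could reach this endpoint. This objection stands in full.

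**The SAP may deal with it.** It may, and the criticism is therefore of the protocol's wording. But the endpoint is defined in the protocol, and that definition omits these opioids rather than leaving them open.

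**Switching may be rare and the bias conservative.** Both are possible and neither is documented. Rescue already has two steps, and no passage names an opioid as the open-label treatment. Endpoint 2 is tested only after both SPI48 comparisons with placebo have succeeded, so those results are untouched and bias in favour of XG005 is the less likely direction. A conservative bias would still cost power and could close the hierarchy.

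**Conclusion.** The point holds as one about wording and prespecification. Endpoints 2 and 3 as written exclude any non-tramadol opioid given between the switch and 48 hours, and the subjects affected are those with inadequate pain control. The tramadol-only total can therefore misstate the between-arm difference in opioid use when switch rate, timing or amount differs by arm. More switching on placebo, with similar use per switcher, would work against XG005.

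Neither the size nor the direction can be determined from the documents. Any number for the bias, including those in the illustration, rests on assumed switch rates and assumed use. Nor do the documents show that the endpoint is biased in this trial or that it must be replaced: if post-switch opioid use is balanced or absent, the mean comparison is unaffected. The primary endpoint is not touched. This is a worthwhile, low-cost improvement, best made before the SAP is finalized.

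**What to change.** 1. Prespecify total opioid consumption in MEQs from end of surgery to 48 hours from all sources: tramadol rescue plus open-label opioids recorded as concomitant medication, with a fixed conversion table. Make it at least a sensitivity analysis for endpoints 2 and 3. Make it the key definition, with tramadol-only as supportive, if the sponsor wants the endpoint to measure opioid sparing.
2. Add a sensitivity analysis that ranks switchers and subjects who leave before 48 hours as worst.
3. Report switch rates and times by arm.
4. State whether tramadol given after the switch counts, and how WOCF applies, if at all, to this cumulative amount.

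**Cost.** A rule in the SAP and a conversion table, plus new endpoint wording in the protocol if the key definition changes. No new data collection is needed: Section 6.5.3 requires concomitant medication to be recorded in the eCRF, and Section 7.4 keeps collecting it after early termination. The downsides are that each opioid needs a conversion factor, that non-opioid open-label analgesics remain uncounted (the worst-rank analysis covers those subjects), and that data may be incomplete for subjects who leave the unit.

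**Separate item.** The Synopsis says that subjects who stop for lack of efficacy "will continue to undergo all safety and pharmacokinetic assessments as scheduled", Section 7.4 limits collection after early termination to safety data, and Section 6.5.4 has subjects given other analgesics leave the study early. These passages should be reconciled on who terminates and which assessments continue. That does not change the MEQ point.

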Study Design:	
This is a multi-center, randomized, double-blind, parallel-group, placebo-controlled study.
 
Subjects scheduled for bunionectomy surgery must meet all of the inclusion criteria and none of the exclusion criteria below prior to being enrolled and randomized.
 
Eligible subjects will be randomized in a 1:1:1 ratio to receive either 750 mg XG005, 1250 mg XG005, or placebo. Randomized subjects will receive drug per their treatment allocation as follows:
 
 
• 60 minutes prior to surgery and every 12 hours (<math>\pm</math> 10 minutes) after the first dose for 72 hours.
 
• Subjects and all study staff performing study assessments will be blinded to treatment allocation. To maintain the blind, a total of 5 tablets will be administered to each treatment group: 5 identical blue tablets (low or high dose XG005 or its placebo) at each time point.
 
 
Subjects will undergo a Screening (Day -28 to Day -1), Pre-Operative Assessment (within 24 hours prior to surgery) and Surgery/Treatment Visit (beginning Day 1), when the following will occur:
 
 
• Study medication administered <math>60 \pm 10</math> minutes prior to surgery, record time.
 
• Surgery performed, record starting time
 
• Record time of end of surgery (as time of last suture closed)
 
• Subjects domiciled in research center for at least 72 hours post-surgery
 
• Efficacy and safety assessments performed over 72-hour period post-surgery
 
 
“Time 0” will be defined as the actual start time of the first dose from which subsequent 12-hour dosing times will be determined. All study efficacy and safety assessments are anchored to time at end of surgery (last suture). Pharmacokinetic (PK) sampling timepoints correlate with the collection of the 11-pt Numeric Pain Rating Scale (NPRS) efficacy assessments when they overlap.
 
Subjects will be advised at Screening that if they terminate the study prior to 72 hours, it is requested that they remain in the clinic for continued collection of scheduled safety data only. Screening will include subjects’ potential placebo response by use of a pre-study personality questionnaire (Appendix B).
 
Subjects will be discharged at a reasonable hour of the day after the end of the 72-hour treatment period, which may include the morning after the end of the 72-hour treatment period.
 
There will be a Follow-up Visit on Day 15.
 
Early Termination visits will include the following assessments: NPRS, Patient Global Assessment (PGA) of pain control, Numeric Nausea Rating Scale (NNRS),

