Safety and PK Endpoints	
Safety
 
Safety and tolerability of XG005 compared with placebo measured by AE reporting (incidence of AEs and SAEs), vital signs, <math>\text{SPO}_2</math>, ECGs, and laboratory values.
 
Sedation will be assessed by study staff by use of the Ramsay Sedation Scale (RSS) when NPRS can be assessed. Nausea will be self-assessed using an 11-point NNRS.
 
Pharmacokinetics
 
Plasma PK parameter endpoints to include the following:
 
 
• Area under the plasma concentration-time curve from time zero to time <math>t</math> of the last measured concentration above the limit of quantification (<math>\text{AUC}_{\text{last}}</math>)
 
• Area under the plasma concentration-time curve from zero to infinity (<math>\text{AUC}_{\text{inf}}</math>)
 
• Maximum plasma concentration (<math>C_{\text{max}}</math>)
 
• Trough plasma concentration prior to each dose (<math>C_{\text{trough}}</math>)
 
• Time to reach maximum plasma concentration (<math>T_{\text{max}}</math>)
 
• Terminal elimination rate constant (<math>\lambda_z</math>) with the respective half-life (<math>t_{1/2}</math>).
 

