## 1.2. Schedule of Assessments

Assessment	Screen	Day 1: Surgery		Treatment Period (Hours Post End of Surgery)											End of Study/Early Termination v
	Days -28 to -1	Pre-Surgery a	Surgery	0	1	2	4	8	12	24	36	48	60	72	
Written Informed Consent b	X														
Inclusion/Exclusion Criteria c	X	X													
Medical History	X	X													
Physical Examination d	X														
Vital Signs e	X	X		X	X	X	X	X	X	X	X	X	X	X	X
Electrocardiogram f	X														X
Clinical Laboratory Testing g	X													X	X
Pregnancy Test h	X	X													X
Urine Drug Screen g	X														
COVID-19 test w	X	X w													
Adverse Events Monitoring i	←————→														
Prior/Concomitant Medications	←————→														
Pre-study personality questionnaire j	X														
C-SSRS Baseline/Screening Version Appendix J	X														

	Screen	Day 1: Surgery		Treatment Period (Hours Post End of Surgery)												End of Study/Early Termination v			
Assessment	Days -28 to -1	Pre-Surgery a	Surgery	0	1	2	4	8	12	24	36	48	60	72	Clinic Visit, Day 15 ( $\pm 2$ )				
C-SSRS Since Last Visit Version Appendix K															X	X			
Patient Health Questionnaire-9 (PHQ-9)	X																		
General Anxiety Disorder (GAD-7)	X																		
Domiciled in Clinic																			
Enrollment/ Randomization		X																	
Study Drug Dosing (XG005 or Placebo) k		X 60 min prior to surgery		Every 12 hours after the first dose defined as "Time 0" for dosing purposes only															
Blood Sample for Pharmacokinetic Assessment l		X Pre-dose			Drawn at 1, 2, 3, 4, 6, 8, 10, 12, 24, 30, 36, 42, 48, 54, 60, 66, and 72 hours ( $\pm 15$ min window) after the end of surgery (last suture) 														
Anesthesia and Bunionectomy Surgery m			X																
Continuous Pulse Oximetry n									X	X	X	X	X	X					
Rescue Medication				PRN															
Numeric Pain Rating Scale (NPRS) p,q					Measure at 0, 1, 2, 3, 4, 6, 8, 10, 12, 16, 20, 24, 30, 36, 42, 48, 54, 60, 66, and 72 hours after the end of surgery ( $\pm 10$ min window)														X (ET only)
Patient Global Assessment (PGA) of Pain Control r										X		X		X			X (ET only)		

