
 
To investigate the PK of XG005, naproxen, and pregabalin in a perioperative population
 
	
 
Area under the plasma concentration-time curve from time zero to time <math>t</math> of the last measured concentration above the limit of quantification (AUC0-last)
 
Area under the plasma concentration-time curve from zero to infinity (AUC0-inf)
 
Maximum plasma concentration (Cmax)
 
Trough plasma concentration prior to each dose (Ctrough)
 
Time to reach maximum plasma concentration (Tmax)
 
Terminal elimination rate constant (<math>\lambda_z</math>) with the respective half-life (t1/2).
 

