### 6.2. Dosing and Administration

Study drug (XG005 low or high dose, or placebo) will be administered as an oral dose 60 minutes prior to surgery on Day 1 then every 12 hours for 72 hours after the time of first dose. The number and strength of active drug tablets to be administered at each dose level is shown in Table 1. Subjects randomized to placebo will receive the corresponding number of placebo tablets.

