## 8. STUDY ASSESSMENTS AND PROCEDURES

Before performing any study procedures, all potential subjects will sign an ICF as outlined in [Section 10.2](#).

All assessments and procedural details during Screening (Day -28 to Day -1), Pre-surgery/Surgery (Day 1), the Treatment Period (hours post end of surgery), and EOS/ET are described in the Schedule of Assessments ([Section 1.2](#)).

All efficacy, safety, and PK assessments are anchored to time at end of surgery (last suture).

Pharmacokinetic (PK) sampling timepoints correlate with the collection of the 11-pt Numeric Pain Rating Scale (NPRS) efficacy assessments when they overlap.

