### **8.3. Pharmacokinetic Assessments**

#### **8.3.1. Pharmacokinetic Sampling and Analysis**

Blood draws will always be performed after each NPRS, nausea, SIS and/or PGA assessment, when applicable, and prior to the first administration of rescue medication. The PK sampling plan uses the post-end-of-surgery schedule to be consistent with the efficacy assessment schedule.

Each subject in the PK subgroup (one site only) will have blood samples drawn for PK assessments at the following time points: prior to the first dose (pre-dose), and post end of surgery at 1, 2, 3, 4, 6, 8, 10, 12, 24, 30, 36, 42, 48, 54, 60, 66, and 72 hours within a  $\pm 15$ -minute window. The actual clock time when the PK sample is collected will be recorded, and the post-dose time for PK analysis will be calculated based on the recorded clock time.

The timing and frequency of PK sample collection is listed in the SOA ([Section 1.2](#)).

Details for the collection, processing, storage, and shipping of PK samples will be provided to the clinical unit separately.

Pharmacokinetic samples will be analyzed using a validated liquid chromatography coupled with tandem mass spectrometry assay for XG005 in human plasma. Assay details, results, and validation will be provided in a separate bioanalytical report.

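### The PK endpoint of a trough before each dose has no matching draw from dose 3 onward, because doses and PK samples run on different clocks

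*Combined protocol and SAP*

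**What the plan says.** The Synopsis (Safety and PK Endpoints) and Section 3 both list "Trough plasma concentration prior to each dose" among the plasma PK parameters.

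Dosing runs on one clock. The Synopsis defines Time 0 as "the actual start time of the first dose from which subsequent 12-hour dosing times will be determined", and Section 6.2 has the first dose 60 minutes before surgery, "then every 12 hours for 72 hours after the time of first dose".

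PK sampling runs on another. Section 8.3.1 places one sample before the first dose and all other scheduled samples "post end of surgery at 1, 2, 3, 4, 6, 8, 10, 12, 24, 30, 36, 42, 48, 54, 60, 66, and 72 hours", each within ± 15 min. The PK row of the Schedule of Assessments (Section 1.2) gives the same list, and Section 8 ties all PK assessments to the last suture. Footnote l of the Schedule gives the reason: surgery times vary, and the PK schedule was meant to match the efficacy schedule. Clock times are recorded, and a separate PK Analysis Plan is announced (Sections 9 and 9.5.4).

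**The concern.** The time from first dose to last suture differs between subjects and is never zero, so a draw at a multiple of 12 h after surgery does not fall just before a 12-hourly dose. If no scheduled sample sits just before a dose, the trough for that dose is not observed, however carefully the protocol is followed. Recorded clock times show when a sample was taken but do not add one. Extra draws before rescue medication follow pain rather than dosing. At stake is whether one named PK endpoint can be reported as defined in the PK subgroup of 90 subjects (30 per arm, so about 60 on active drug).

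**Working it through.** The plan gives no figure of its own to reproduce, so the check is a timeline.

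**Inputs**
- Lead from first dose to start of surgery: 60 ± 10 min (Synopsis, Study Design).
- Surgery: at most 90 min (Section 6.5.5). Minimum of 20 min: assumed.
- Dose window ± 10 min (Synopsis, Section 4.1); PK draw window ± 15 min (Section 8.3.1).
- The 17 post-surgery draw times in Section 8.3.1.

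**Offset.** Let D be the time from first dose to last suture.
- Minimum: 50 + 20 = 70 min = 1.17 h.
- Maximum: 70 + 90 = 160 min = 2.67 h.

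**Gaps.** On the first-dose clock, dose k is at 12(k − 1) h and the draw labelled T is at T + D. The gap is the dose time minus the latest draw not after it.

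| Dose | Time (h) | Last prior draw | Gap | Range (h) |
|---|---|---|---|---|
| 2, D ≤ 2 h | 12 | T = 10 | 2 − D | 0–0.83 |
| 2, D > 2 h | 12 | T = 8 | 4 − D | 1.33–2.00 |
| 3 | 24 | T = 12 | 12 − D | 9.33–10.83 |
| 4, 5, 6 | 36, 48, 60 | T = 30, 42, 54 | 6 − D | 3.33–4.83 |
| 7, if given | 72 | T = 66 | 6 − D | 3.33–4.83 |

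**Windows.** A draw 15 min late and a dose 10 min early shorten a gap by 25 min (0.42 h).
- Minima become 9.33 − 0.42 = 8.9 h (dose 3) and 3.33 − 0.42 = 2.9 h (doses 4 onward).
- For dose 2, the 10 h draw can fall after the dose once 10 + D + 0.25 > 12 − 0.17, that is, once D exceeds about 1.6 h.

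**The 24, 36, 48 and 60 h draws.** These fall D = 1.2–2.7 h after doses 3, 4, 5 and 6. Windows could put one before its dose only if D were 25 min or less, and the Synopsis lead alone is at least 50 min. Section 4.1 words the lead differently, with surgery no more than an hour after the first dose. Taking that as a lead of 0–60 min, D is 0.33–2.50 h and the gaps are 9.5–11.7 h (dose 3) and 3.5–5.7 h (doses 4 onward). The 25-min exception then becomes possible, but only for very short intervals.

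**Can an earlier draw stand in?** Illustrative one-compartment model, six equal doses: each dose contributes ka/(ka − ke) × [exp(−ke·u) − exp(−ka·u)] at time u after it.
- Tmax is 4 h (Section 4.2). Half-life is 12–17 h (Section 4.3), which describes naproxen itself, not naproxen formed from XG005.
- ke = ln 2 / half-life. Solving ln(ka/ke)/(ka − ke) = 4 gives ka = 0.67/h (12 h) and 0.78/h (17 h).

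Results over D = 1.17–2.67 h:
- Last prior draw divided by true trough: 1.15–1.49 (dose 3) and 1.14–1.31 (doses 4–6).
- 24–60 h post-dose draws divided by the trough before that dose: 1.33–1.78.
- Last prior draw carried forward, C × exp(−ke × gap), with ke taken as known: within 1% of the trough for doses 4–6, but 9–33% too low for dose 3.

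Dose 3 fails because its last prior sample is only 1.2–2.7 h after dose 2, while concentrations are still rising towards the 4 h peak.

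**The case against.** The anchoring is deliberate and its reason is stated. Actual times are recorded, parameters are to be calculated from actual sampling times (Section 9.5.4), and a PK Analysis Plan that is not among the documents may define how the trough is obtained. Neither endpoint list says the trough must be observed rather than derived. No test, decision rule or sample size uses it, and multiple-dose PK was already studied in Phase 1 (Section 2.3).

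Much of this stands. A reader might infer that no analysis could produce a trough for any dose from the third onward. The documents do not support that: samples at 30, 42 and 54 h lie in the declining part of the interval and can be carried forward to doses 4–6. The 1% figure assumes a known elimination rate, so a real analysis would be less precise, but the route exists.

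Two things do not fall to the objection. The documents nowhere say the trough will be derived this way, and for dose 3 the simple derivation does not work.

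**Conclusion.** The concern holds as a minor inconsistency between a named PK endpoint and the sampling schedule. Dose 1 has a true pre-dose sample and dose 2 a near-trough by coincidence. Doses 4–6 have samples 3.3–4.8 h early from which a trough could be derived. Dose 3 has nothing usable in the 9.3–10.8 h before it (at least 8.9 h with windows). The gap ranges rest on the Synopsis lead and the assumed 20-min minimum surgery; the lower ends do not depend on that assumption. The percentages rest on an illustrative model using naproxen's own half-life.

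Three further readings are tempting but unsupported:
- That the 12-hourly draws are meant to be reported as troughs. Nothing in the documents plans this; the ratios only show that they could not serve.
- That only XG005 is assayed, because Section 8.3.1 refers to a "tandem mass spectrometry assay for XG005 in human plasma". Footnote l of the Schedule says all three analytes are measured, and how AUCinf and the terminal rate apply to each is a matter for the PK Analysis Plan.
- That efficacy is affected. SPI48 does not use these samples.

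**What to change.** In the PK subgroup, in all arms so that the blind is kept, take a few existing draws immediately before the actual dose and record both clock times. One workable set is the 10 h draw before dose 2, the 8 h draw before dose 3 and the 54 h draw before dose 6. Then either restrict the trough endpoint in the Synopsis and Section 3 to the doses with a pre-dose draw, or state that the remaining troughs are model-derived from actual times. Amend the matching sampling text in the Synopsis, the Schedule of Assessments with footnote l, and Sections 4.1, 8 and 8.3.1.

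The Synopsis and Section 4.1 must be reconciled on the interval between first dose and surgery. The protocol must also say whether a dose falls at 72 h, which the Section 6.2 wording leaves open. Both determine which doses need a pre-dose draw; a seventh dose would lack one too.

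**Cost.** There are no added draws or visits, and the NPRS schedule is unchanged. Three of the 17 post-surgery draws no longer coincide with an NPRS rating; 14 still do. In the same six-dose model, linear-trapezoid AUClast moves from about 2–5% too high to 0.5–3% too low, and the share of Cmax captured stays at 91–100%. Moving five draws (10, 8, 30, 42 and 54 h) would cover doses 2–6 but costs more: AUClast about 4–8% too low, and five draws off the NPRS times.
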